Vigabatrin capsules will be taken by participants daily for 30 days. Drug tablets will be administered orally as provided by the manufacturer and dosage matching the FDA label. Specifically, we will provide each patient with a total dosage of 44.5 g vigabatrin. Subjects will be instructed to take one 500 mg pill 2X/day for the first 7 days (days 0-6; 1000 mg/day), 1 pill in the morning and 2 pills in the evening for days 7-13 (1500 mg/day), and two pills 2X/day for days 14-23 (2000 mg/day). On day 24, participants will initiate a step-down protocol as recommended by the manufacturer, moving to the one pill 2X/day dose for days 24-30, before discontinuing treatment. Study participants will meet with the research coordinator or one of the investigators weekly to ensure compliance with the study protocol and problem-solve any barriers. Regular medical monitoring by the study research coordinator and medical staff will be performed during the entire study period. Subjects will be asked to come in weekly while on the drug. At the visit, a general wellness check (including depression screening with the Beck Depression Inventory-II³⁰), vital signs and body weight and a urine drug test will be obtained, and blood samples (7 ml of blood (~0.5 tablespoon)) will be obtained at the weekly visit for the first two weeks of dose escalation to assess routine laboratory tests. Study participants will be instructed to keep their body weight stable (< 2% change) during the treatment period.

Dispensing and accountability

A medication accountability log will be used to document dispensing of the vigabatrin to the participant and the return of unused product by the participant. The medication accountability log will document the participant ID, initials, the amount of medication and the date the drug was dispensed to the participant, and the amount of medication that the study participant returned. Participants will be instructed to return unused medications at every scheduled study visit and study end. The study research coordinator will perform a pill count and document this in the medication accountability log at each study visit.

Repeat studies

The HEC procedure and mOGTT performed at baseline as well as the MRI to determine liver triglyceride content at screening will be repeated after 3 weeks of treatment. In addition, depression measured with the Beck Depression Inventory-II³⁰ (measured at screening) will be re-assessed at the repeat mOGTT.

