infection. The total amount of blood collected during the full set of research procedures will be ~500 mL including all screening, baseline, post-treatment and medical monitoring visits . If a participant develops a health problem or potential health problem, the PI/study physician and, if necessary a medical consultant who is not part of the research team, will decide whether the participant should be continued in the study, and/or what further steps regarding medical evaluation/treatment should be performed. The CTRU and hospital facilities used for the study are equipped with defibrillators and all appropriate emergency medications. Should the need for medical treatment arise, the PI/study physician will arrange for medical evaluation at the Washington University School of Medicine, which provides all the resources of a large teaching hospital for subject evaluation and treatment. The subject and the primary care physicians will be made aware of any abnormal findings while participating in the study. The participants will be given the phone numbers of the members of the research team (including an emergency phone number) and told to call a member of the research team immediately if they develop any unusual signs or symptoms. Subjects will be screened for depressive symptoms before starting treatment, while on treatment and at study completion. If the subject reports significant increase in depression or thoughts of suicidal ideation, the subject will be removed from the study and immediately be sent for psychiatric evaluation. Vision testing will be completed in all subjects at baseline, after a week at the maximum dose and then 6 months after drug initiation. If vision changes are noted, subjects will be referred for further testing and evaluation by an ophthalmologist.

Potential benefits of the research to the participants

Potential benefits to the participants include obtaining information regarding their body composition and a medical examination. Participants' basal measures of glucose homeostasis may improve with this treatment. These results could support the findings from studies conducted in rodent models and lead to a new approach for treating metabolic abnormalities in people.

Importance of the knowledge to be gained

The information gained from this work has important public health implications in the potential of development of a new drug for treatment or prevention of NAFLD.

Data and safety monitoring plan

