Data from the study will be monitored on a continual basis by the PI. All serious adverse events (SAEs), adverse events (AEs), and laboratory values will be reviewed by the PI on an ongoing basis. The PI will be responsible for annual reports to Washington University School of Medicine's IRB and for reporting any adverse events to the IRB.

The IRB at Washington University School of Medicine defines unanticipated problems (adverse events) as involving risks to participants or others which are: 1) unexpected (in terms of nature, severity, or frequency) given (a) the research procedures that are described in the study-related documents, such as the IRB-approved research study and informed consent document; and (b) the characteristics of the subject population being studied; and 2) are related or possibly related to participation in the research; and 3) suggest that the research places participants or others at a greater risk of harm (including physical, psychological, economic, or social harm) than was previously known or recognized.

Adverse events will include vision loss, suicidal behavior, anemia, peripheral neuropathy, edema, ear disorders: deafness, gastrointestinal disorders, hepatobiliary disorders (cholestasis), nervous system disorders (dystonia, encephalopathy, hypertonia, hypotonia, muscle spasticity, myoclonus, optic neuritis), psychiatric disorders (acute psychosis, apathy, delirium, hypomania, neonatal agitation, psychotic disorders), respiratory disorders (laryngeal edema, pulmonary embolism, respiratory failure, stridor skin), and/or subcutaneous tissue disorders (angioedema, maculo-papular rash, pruritus, Stevens-Johnson syndrome (SJS), toxic epidermal necrolysis (TEN))

Adverse Event Reporting: All AEs will be graded according to the following scale:

- 0 = No adverse events or within normal limits
- 1 = Mild; did not require treatment
- 2 = Moderate; resolved without treatment
- 3 = Severe; required professional medical attention
- 4 = Life-threatening or disabling

5 = Death

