The PI will review AEs and notify the IRB of any changes needed to the protocol. The IRB will be notified within 24 hours of any SAE (grade 4 or 5) occurring at this site via their online system for reporting SAEs, and additional information will be forwarded to the IRB as it becomes available. AE's (grades 2-3) will be reported by the PI to the IRB within 10 working days. Mild AE's (grade 1) will be reported at the annual continuing review. In addition, all laboratory values outside of the normal range will be discussed with the study participant, and appropriate arrangements will be made for treatment, if necessary. The annual summary of all adverse events and any audit reports will be sent to the IRB at the time of continuing review.

If the data received during the course of the study on a study participant indicate they he or she may benefit from (other) medical intervention, then the appropriate recommendation(s) and/or consultation(s) will be made.

A Data and Safety Monitoring Board, chaired by [name] MD (Professor of Medicine), and including [name] (Associate Professor of Medicine) will meet every 12 months with the PI, Co-Investigators, and the study research coordinator, to review study data, discuss any safety issues, and ensure compliance with the protocol.

Study Withdrawal/Discontinuation

Participants are free to withdraw at any time. Female participants who become pregnant will be removed from the study. If the participant's doctor decides that staying in the study places the participant at risk, she/he will be withdrawn. Any condition deemed by the study personnel to interfere with the participant's ability to complete the study will be cause for withdrawal. Subjects will be removed from study if they no longer meet the study criteria, if an SAE occurs, if they do not show up to study visits, or if the study is terminated.

Subjects that are removed or withdraw from the study will initiate the drug step-down protocol by decreasing their drug dose by 1000 mg for one week prior to stopping the drug completely.

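### Serious adverse events are identified only by severity grade, so a hospital admission graded 3 gets a 10-working-day IRB report instead of a 24-hour one (minor)

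*Combined protocol and SAP*

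**What the plan says.** Under *Data and safety monitoring plan*, the protocol spells out the abbreviation when it assigns review to the principal investigator: "All serious adverse events (SAEs), adverse events (AEs), and laboratory values will be reviewed by the PI on an ongoing basis". It gives no criteria for seriousness there.

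The *Adverse Event Reporting* scale runs from 0 to 5. The two steps that matter here are "3 = Severe; required professional medical attention" and "4 = Life-threatening or disabling". Grade 5 is death.

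Three reporting clocks follow. The fastest is "The IRB will be notified within 24 hours of any SAE (grade 4 or 5) occurring at this site". The next is "AE's (grades 2-3) will be reported by the PI to the IRB within 10 working days". Grade 1 events wait for the annual continuing review.

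The term is used once more, under *Study Withdrawal/Discontinuation*: "Subjects will be removed from study if they no longer meet the study criteria, if an SAE occurs". No section lists hospital admission, or any other outcome apart from those built into grades 4 and 5, as making an event serious.

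**The concern.** Severity describes how intense an event is. Seriousness describes what it led to. The plan uses the first in place of the second. The two usually agree at the extremes, but they part company in the middle: a participant can be admitted to hospital with an event that neither threatens life nor leaves a disability. Under this plan such an event is routed with the non-serious ones.

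What is at stake is how soon a body outside the study team hears of it. Prompt outside notice serves other participants as well as the one affected, because it lets someone independent ask whether the study should carry on unchanged. The trigger for that notice is grade alone.

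**Working it through.** The plan states no figure to reproduce. The check is a reading of the scale against the clocks, followed by a day count.

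**Step 1: grade of an admission.** Take an admission that does not threaten life, does not disable and is not fatal. It fails the wording of grades 4 and 5. It did need professional medical attention, which is the grade 3 descriptor. It is therefore at most grade 3.

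**Step 2: clock for that grade.** The grade parenthesis in the 24-hour sentence can be read in three ways.

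- As a definition (serious means grade 4 or 5), the admission is not an SAE and takes the 10-working-day clock.
- As a restriction (only those SAEs that are grade 4 or 5), the admission may be an SAE but is outside the 24-hour rule, and again takes the 10-working-day clock.
- As an illustration, a grade 3 SAE would fall under both sentences and the plan would not say which governs. No other definition of SAE exists to support this reading.

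**Step 3: other routes to faster notice.**

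- The IRB definition of unanticipated problems, quoted in the monitoring plan, carries no reporting time and does not mention admission.
- The Data and Safety Monitoring Board meets yearly.
- The principal investigator's ongoing review is internal to the study team.
- The IRB's own reporting policy is not in the document.

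**Step 4: length of the delay.** Assumptions: the investigator learns of the event on the day it happens, counting starts the next day, there are no public holidays, and the full limit is used.

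| Day of event | Tenth working day falls after | Minus the 24-hour limit |
|---|---|---|
| Monday to Friday | 14 calendar days | 14 − 1 = 13 days later |
| Saturday | 13 calendar days | 13 − 1 = 12 days later |
| Sunday | 12 calendar days | 12 − 1 = 11 days later |

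For example, after a Monday event the first four working days end on Friday (day 4), the next five fill the following week (days 7 to 11), and the tenth is the Monday after that (day 14). After a Sunday event the ten working days fill two weeks and end on Friday (day 12).

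The report can thus arrive 12 to 14 calendar days after the event, which is 11 to 13 days later than the 24-hour rule would allow.

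**The case against.** The strongest reply is that nothing in the protocol says an admission of this kind is serious or needs 24-hour notice. That standard comes from the usual distinction between seriousness and severity. The plan states a rule and applies it consistently. This stands: it is a design choice and not an internal contradiction, and a reader should not infer one.

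It can also be said that the IRB has rules that are not visible here. The protocol quotes one IRB definition and refers to an IRB online system for serious events, so a faster duty may exist outside the document. That too stands. A faster route can be neither assumed nor excluded, so one should not infer that the IRB will in practice hear late, only that this plan permits it. Ten working days is a maximum, and the investigator may report sooner.

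Two stronger readings are tempting.

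- *The delay puts the participant's care or dosing at risk.* The documents do not support this. Decisions on continuing and on treatment rest with the investigator or study physician, with an outside consultant where needed, and no section makes care or dosing wait for the IRB. Setting the reporting limit against the dosing calendar therefore measures little.
- *A psychiatric admission shows the gap at its worst.* For significantly increased depression or suicidal ideation the plan says "the subject will be removed from the study and immediately be sent for psychiatric evaluation". Such a participant is already out of the study, and an admission that followed could well be graded life-threatening, which carries the 24-hour report. It is a possible case but not a telling one.

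Finally, with 6 participants, weekly visits on drug and continual review by the investigator, few or no such events may occur. That lowers the weight of the point. It does not answer it, because the rule as written still sends a serious event of grade 3 or below to a slower clock.

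**Conclusion.** The point holds as a minor gap in oversight. The plan identifies a serious event only by grade 4 or 5 and gives all grade 2 and 3 events 10 working days. An event with a serious outcome that is not life-threatening, disabling or fatal may therefore be reported to the IRB up to 12 to 14 calendar days after it happens instead of within 24 hours.

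The reading of the scale and clocks is firm. The size of the delay rests on same-day awareness, no holidays and use of the full limit. The view that admission should count as serious rests on common practice and not on the protocol's text.

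The consequence is limited to how promptly an independent body is told, including for the protection of other participants. All graded adverse events still reach the IRB eventually, immediate care does not wait for the report, and the effect-size estimate is not affected.

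**What to change.** Define a serious adverse event in the monitoring plan by outcome and independently of grade: death, threat to life, disability, hospital admission, and any other outcome the sponsor chooses to list. Apply the 24-hour IRB report to every event that meets the definition, whatever its grade. Keep the 10-working-day and annual clocks for non-serious events.

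The removal sentence under *Study Withdrawal/Discontinuation* relies on the same term, and removal starts the step-down procedure. A wider definition would therefore widen that trigger too unless the sentence is addressed. The sponsor must reconcile it in the same amendment and state what is intended; no removal or step-down rule is proposed here.

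The cost is one definition, one revised reporting sentence, the reconciliation just described, and a few more 24-hour reports. No analysis, visit or sample size changes.

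### The step-down rule after removal has no safety exception, so a forced removal on days 7-23 continues vigabatrin for another week

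*Combined protocol and SAP*

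**What the plan says.** Under Study Withdrawal/Discontinuation, "Subjects that are removed or withdraw from the study will initiate the drug step-down protocol", and the step-down consists of "decreasing their drug dose by 1000 mg for one week prior to stopping the drug completely". The sentence covers everyone who leaves, for whatever reason.

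Three routes to removal are driven by safety:

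- **SAE.** The same section states: "Subjects will be removed from study if they no longer meet the study criteria, if an SAE occurs". The Data and safety monitoring plan ties an SAE to the top two grades: "The IRB will be notified within 24 hours of any SAE (grade 4 or 5) occurring at this site". Grade 5 is death, so grade 4 (life-threatening or disabling) is the case that matters here.
- **Physician's judgement of risk.** If the participant's doctor "decides that staying in the study places the participant at risk, she/he will be withdrawn".
- **Depression or suicidal ideation.** In the paragraph on medical risks, under Adequacy of protection against risks: "If the subject reports significant increase in depression or thoughts of suicidal ideation, the subject will be removed from the study". Immediate psychiatric evaluation follows. What happens to the study drug is not stated.

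The Intervention section gives the dosing schedule: 1000 mg/day on days 0-6, 1500 mg/day on days 7-13, 2000 mg/day on days 14-23, and a manufacturer-recommended step-down to 1000 mg/day on days 24-30. The stated total is 44.5 g.

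**The concern.** The protocol expects that some events leading to removal may be caused by the drug. Potential Risks names depression and suicidal thoughts among the side effects of vigabatrin. The Data and safety monitoring plan lists suicidal behavior, angioedema, laryngeal edema, Stevens-Johnson syndrome and toxic epidermal necrolysis among the adverse events. For such events a physician may want the drug stopped that day.

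The only sentence on drug handling after removal directs a step-down instead. Staff who follow it exactly may keep a participant on the suspected drug for a further week. A physician who stops at once departs from the written instruction. What is at stake is the safety of one or a few participants and clarity for site staff, not the trial's estimates.

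**Working it through.** **Inputs.** Daily doses and day ranges come from the Intervention section. The size (1000 mg) and length (one week) of the step-down come from Study Withdrawal/Discontinuation.

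**Step 1: reproduce the planned total.** Sum of days × daily dose:

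7 × 1.0 g + 7 × 1.5 g + 10 × 2.0 g + 7 × 1.0 g = 7 + 10.5 + 20 + 7 = 44.5 g, over 31 dosing days. This matches the stated figure.

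**Step 2: drug taken after removal under the literal rule.** Further drug = (current daily dose − 1000 mg) × 7 days.

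| Day of removal | Dose at removal | Dose in the following week | Further drug | 500 mg pills |
|---|---|---|---|---|
| 0-6 | 1000 mg/day | 0 | 0 g | 0 |
| 7-13 | 1500 mg/day | 500 mg/day | 3.5 g | 7 |
| 14-23 | 2000 mg/day | 1000 mg/day | 7 g | 14 |
| 24-30 | 1000 mg/day | 0 | 0 g | 0 |

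The rule is therefore already an immediate stop on 7 + 7 = 14 of the 31 dosing days. Drug continues after removal only on the other 7 + 10 = 17 days, days 7-23.

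**Step 3: largest total exposure after a removal in that window.** Cumulative dose at the end of day 13 is 7 + 10.5 = 17.5 g, and at the end of day 23 it is 17.5 + 20 = 37.5 g.

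- Removed at the end of day 13: 17.5 + 3.5 = 21 g.
- Removed at the end of day 23: 37.5 + 7 = 44.5 g.

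Neither exceeds the planned total.

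**Step 4: look for an exception in the text.** The step-down sentence contains none. The suicidal-ideation sentence requires removal and psychiatric referral but is silent on the drug. The general provisions on medical decisions, discussed under the objection, do not refer to the step-down.

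**The case against.** The strongest reply is that the discretion already exists. For any health problem, actual or potential, the paragraph on medical risks lets the PI/study physician, with an outside consultant if needed, decide on continuation in the study and on further medical evaluation or treatment. The same paragraph uses the word treatment for vigabatrin when it describes depression screening, so the power can be read to cover stopping the drug. The Data and safety monitoring plan adds that, where a participant may benefit from medical intervention, "then the appropriate recommendation(s) and/or consultation(s) will be made". The safety routes also lead quickly to clinicians, and a participant may withdraw at any time. This stands in part: an override is plausible, and that lowers the severity. But a general power beside a specific instruction that does not mention it leaves room for doubt about whether an immediate stop is a deviation.

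A second reply is that the taper is recommended by the manufacturer and that nothing in the documents shows abrupt stopping to be safer. That also stands. It supports keeping the taper as the default and making any exception permissive.

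A reader might infer several stronger points that the documents do not support:

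- **Every removed participant takes drug for another week.** Not on the literal rule, which gives 0 mg on days 0-6 and 24-30.
- **The step-down is to 1000 mg/day, so early removals also continue.** That target belongs to the planned taper on days 24-30. For removed participants the text says by 1000 mg. The planned change from 2000 to 1000 mg/day is itself a cut of 1000 mg, so the two sections do not conflict.
- **The extra week threatens vision through cumulative dose.** Potential Risks reports no evidence of a visual effect below 1 kg, and 44.5 g is 44.5/1000 = 4.45% of that.
- **Pregnancy needs its own exception.** "Female participants who become pregnant will be removed from the study", but the documents describe no pregnancy-specific hazard of vigabatrin.

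**Conclusion.** The point holds, at low severity. For a removal forced by an SAE or suicidal ideation on days 7-23, the written rule continues a suspected drug for a week: 3.5 g more from 1500 mg/day, or 7 g more from 2000 mg/day. Outside those days it already stops the drug at once.

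This rests on reading the 1000 mg reduction literally and on the step-down sentence governing where no other text qualifies it. The gram figures describe exposure only. The documents give no figure linking one more week of vigabatrin to a psychiatric or other event. With six participants seen weekly while on drug, few are likely to be affected, possibly none. No endpoint, effect-size estimate or planned analysis is touched.

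**What to change.** Keep the step-down as the default and add one clause to the sentence in Study Withdrawal/Discontinuation: *unless the PI/study physician directs immediate discontinuation, for example for an SAE or a suspected drug reaction, including suicidal ideation*.

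The cost is one clause in an amendment. The downside is abrupt stopping, whose risk the documents do not quantify, in the few participants for whom the physician judges it safer than a taper. The clause mandates no abrupt stop and changes nothing for participants who complete or who leave for other reasons.

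Stating the resulting step-down dose in mg/day for each stage would be a useful but optional clarification. I would not add a pregnancy clause, for the reason above, or new record-keeping: the documents show no harm from its absence, and the Intervention section already requires an accountability log and pill counts.
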